The design size contemplates enrolling up to one hundred and twenty (120) subjects who will successfully follow through to completion of their participation in at least the first treatment portion of the study (first 3-month treatment period). The subjects will be randomly assigned to: twice-per-day active, once-per-day active or twice-per-day placebo in a 1:1:1 ratio.

The results of the first migraine RCT did not show evidence of stratification based on gender or clinical site or baseline headache frequency. Envelopes containing

randomization assignments will be grouped in batches of six, each batch containing two of each of the three assignment arms. The batches of envelopes will be randomly shuffled by an agent not involved with the study. A given batch will be completed before the next batch is opened. This procedure results in 20 possible different arrangements, for six subjects, of the ordering of treatment and placebo assignments. The unblinded coordinator will record the subject's designation but will not share the assignment with the subject, principal investigator, or statistician. Each study site will be individually randomized (no central randomization).

The assessment of the primary endpoint will be completed by a blinded, central statistician. The subjects will be told, within the informed consent document, of the existence of a placebo arm. Subjects will be told that the device stimulates the brain stem. Subjects will be told that they will receive at least 3-months of active treatment during the 6-month treatment period. In fact, subjects in the placebo arm in the first 3-month period will be switched to active in the second 3-month period. Subjects will be asked to guess (and provide reasons) about their treatment assignment at the end of the first 3-month treatment period and at the end of the second 3-month treatment period. Subjects will also be asked, after their very first treatment in the clinic, a series of questions designed to assess the quality of blinding (to provide evidence that the placebo device is an effective sham).

4) Study Schedule; Subject Enrollment and Activities

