An experienced, independent and blinded Statistician will analyze and summarize the daily headache diaries for all subjects and evaluate the primary endpoint and observational aims. A blinded reviewer will analyze and summarize the quality of life data.

The primary aim of this trial is to determine if subjects randomized to the twice-daily active group, have a greater reduction in the number of headache days than those assigned to the twice-daily placebo group. For this study, the reduction in headache days (primary endpoint) is calculated as the number of headache days during the baseline month minus the number of headache days during treatment month three. An intent-to-treat methodology will be employed for the primary aim; however, per protocol analyses will also be conducted for comparison. Analysis of the primary endpoint and the secondary headache-related endpoints assessed in the daily diary will be performed for all subjects that complete at least 25 diary entries or more during the relevant 28-day treatment month. Treatment compliance is defined as completion of at least 50% during

each treatment months (for the per protocol evaluation). Subjects with treatment compliance below 50% during any treatment month will be assigned to the intent-to-treat group only. As accurate assessment of some of the secondary endpoints assessed during study period do not depend on daily headache diary compliance, treatment compliance will be the only criteria for inclusion in the per protocol analysis of those secondary outcomes. Statistical significance will be defined with a Type I error of 5% ($\alpha=0.05$). Wilcoxon rank-sum tests (for non-normal data) or a paired student's t-tests (for normal data) will be used to establish whether the reductions in headache days between the baseline and third treatment month in each treatment arm are statistically significant. Mann-Whitney U tests (for non-normal data) or unpaired student's t-tests (for normal data) will be used to determine whether the reduction in migraine headaches in the twice daily active treatment arm subjects is significantly greater than that observed in the twice daily placebo treatment arm subjects. No interim analyses of efficacy are planned.

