The study is powered for the primary aim. Given a sample size of 40 subjects per arm and a standard deviation in the reduction of headache days of $\sigma=3.36$, a mean difference for the reduction in the number of headache days between the twice-daily active arm and the twice daily placebo arm of 2.13 days will be detectable at the 95% significance level ($\alpha=0.05$) with 80% power. The figure below shows the sensitivity of the detectable differences relative to the value of the standard deviation and the sample size.

The study is intentionally overpowered for the primary endpoint (based on the mean reduction of 2.73 headache days in the first RCT), however, a sample size of 40 subjects per arm should allow for sufficient power to assess the majority of secondary endpoints at

the end of the sixth treatment month and at the end of the post-treatment observation period given the expected dropout rate of 5 subjects per group during each 3 month period. Notably, while the 50% responder rate (a secondary outcome) will be evaluated as a discrete variable, it is unlikely to yield statistical significance due to insufficient sampling. Therefore, the similar measure of percent-change in migraine days will also be compared as a continuous variable across groups.

An analysis will be conducted to determine if blinding was successful using descriptive statistics.

9) Quality Assurance Monitor

A quality assurance monitor will be used to audit study sites. Following written procedures, the monitor will verify that the clinical trial is conducted and data are generated, documented and reported in compliance with the protocol, GCP and applicable regulatory requirements. Investigational site(s) will provide direct access to all trial related sites, source data/documents and reports for the purpose of monitoring and auditing by the sponsor and inspection by regulatory authorities.

10) Procedures for adverse events:

- **Documentation and assessment**
 - Following the informed consent process, clinical study subjects will be routinely questioned about adverse events at study visits and telephone contacts by the clinical research sites. All adverse events, regardless of treatment group, or suspected causal relationship to the investigational device, will be recorded in the subjects' case report forms in their study binder.

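### The primary test is valid, but it leaves out baseline as a covariate and the site stratum and names no single method; adjustment costs little, and its gain is uncertain

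*Combined protocol and SAP*

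**What the plan says.** Section 8 (Statistical Analysis and Study Size) defines the primary variable as a change score, "calculated as the number of headache days during the baseline month minus the number of headache days during treatment month three". For twice-daily active against twice-daily placebo it offers "Mann-Whitney U tests (for non-normal data) or unpaired" t-tests, which "will be used to determine whether the reduction in migraine headaches in the twice daily active treatment arm subjects is significantly greater" than in the placebo arm. It gives no normality test, no cut-off, no statement of whether the check is per arm or pooled, and no time at which the choice is made. The test has no covariate or stratum term. Alpha is 0.05 and sidedness is not stated.

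The sizing paragraph of Section 8 is built on "a mean difference for the reduction in the number of headache days between the twice-daily active arm" and the placebo arm: 2.13 days, SD 3.36, 40 per arm, 80% power. It calls the study deliberately overpowered, citing 2.73 days from the first RCT.

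Section 3 (Pivotal Study Size; Randomization) randomizes each site separately, in batches of six with two envelopes per arm. It reports that the first RCT "did not show evidence of stratification based on gender or clinical site or baseline headache frequency". It adds: "The assessment of the primary endpoint will be completed by a blinded, central statistician". Section 8 likewise says: "An experienced, independent and blinded Statistician will analyze and summarize the daily headache diaries".

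Section 7 words the primary endpoint in migraine headache days. The Section 8 formula and the sizing use headache days.

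**The concern.** A change score fixes the slope of month 3 on baseline at 1. If the true slope is lower, part of the baseline variation stays in the outcome as noise, and a model with baseline as a covariate would remove it. Allocation is blocked within site, so site is part of the design and would normally appear in the analysis. Both items are collected anyway, and the plan uses neither.

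The primary test is also not a single named method. Two tests are listed, and the rule for choosing between them has no criterion. At stake are some precision, an analysis that matches the randomization, and a primary p-value that cannot be questioned later for how its test was picked.

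**Working it through.** **1. Reproduce the plan's figure.** Inputs from Section 8: n = 40 per arm, SD 3.36, alpha 0.05.
- Standard error = 3.36 × √(2/40) = 0.751. Noncentral t, 78 df.
- Two-sided: power 79.95% at 2.13 days, detectable difference 2.131 days. The stated figure reproduces.
- One-sided: power would be 87.8%, so the sizing is two-sided.
- Power at 2.73 days is 94.8%. The 95% CI half-width is 1.991 × 0.751 = 1.50 days.

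**2. Validity of the planned tests.** Simulation under no effect, 40 per arm, 40,000 trials per setting. Assumed: baseline mean 8, SD 2.5, placebo drop of 1 day; either normal data, or rounded counts with baseline held to 4-14 and month 3 floored at 0.
- t-test: 4.9-5.1%. Mann-Whitney: 4.7-5.0%. ANCOVA: 4.9-5.1%.
- Normality rule fixed in advance (assumed Shapiro-Wilk at 5%; 4,000 trials per setting, Monte Carlo SE 0.35 point): 4.9-5.5%. A separate run of 20,000 trials on each of five null shapes gave 5.0-5.3%.
- Taking the smaller p-value, which the plan does not permit: 5.7-6.0%, and 6.0-7.0% over the five shapes.
- Site left out (8 assumed sites, 8,000 trials): 5.3%, 4.8%, 4.0% and 3.3% at an assumed intraclass correlation of 0, 0.05, 0.1 and 0.2. If sites differ, the omission makes the test conservative.

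**3. Effect of a baseline covariate.** Residual variance = 3.36² − (1 − slope)² × (baseline SD)², with 77 df. Example at slope 0.5 and SD 2.5: 11.29 − 0.25 × 6.25 = 9.73, so residual SD 3.119. Baseline SD and slope are assumptions.

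| Slope | Residual SD (baseline SD 2.5) | Power at 2.13 days | Power at 2.73 days | CI half-width (days) | Power at 2.13 days (baseline SD 2.0) |
|---|---|---|---|---|---|
| 1.0 | 3.360 | 79.9% | 94.8% | 1.50 | 79.9% |
| 0.8 | 3.323 | 80.8% | 95.2% | 1.48 | 80.5% |
| 0.5 | 3.119 | 85.5% | 97.2% | 1.39 | 83.5% |
| 0.3 | 2.868 | 90.6% | 98.7% | 1.28 | 86.8% |

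These values ignore chance baseline imbalance. In simulation at slope 1.0, ANCOVA lost 0.3 to 0.5 point against the t-test (79.3% against 79.8% with normal data; 77.9% against 78.2% with counts).

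**4. Cost of a site term.** If sites do not differ, going from 1 to 12 assumed sites lowers power at 2.13 days from 79.94% to 79.77% at slope 1.0, and from 85.45% to 85.30% at slope 0.5.

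**5. How often the choice of test matters.** With 2.13 days entered, the t-test and Mann-Whitney fall on different sides of 0.05 in about 5% of trials (4.8-5.2%). This is a rate of disagreement, not an error rate.

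**The case against.** The strongest reply is that nothing here is broken. The unadjusted comparison is valid. At 2.73 days there is little power left to gain on 94.8%, and every gain rests on figures that the documents do not contain. The first RCT showed no sign that site or baseline frequency called for stratification. All of this stands as a limit on the benefit. The sentence about the first RCT concerns stratification, however. It does not show that baseline counts fail to predict month-3 counts, and it does not remove the blocking by site from the design.

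A reader might infer two stronger points, and the documents support neither.
- **That the open choice of test inflates type I error.** Section 8 ties the choice to normality, not to the smaller p-value. When the rule is followed the error stays near 5%. A rate of 5.7% or more needs a departure from the plan, and the statistician is described as independent and blinded.
- **That the target of estimation is undefined.** Section 7 words the endpoint as an average, and Section 8 sizes a mean difference. The quantity is a difference in mean reduction, which can be reported whichever test supplies the p-value. Only the test is open.

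**Conclusion.** The planned comparison is valid, and the 2.13-day figure stands. Leaving out the baseline covariate and the site stratum is a missed improvement at low cost, not an error. Its size cannot be settled from the documents. At 2.13 days and an assumed baseline SD of 2.5, it runs from a loss of up to about 0.5 power point at slope 1 to a gain of about 10.6 points (90.6 − 80.0) at slope 0.3. The range follows from the slopes chosen. At 2.73 days there is little left to gain, and no gain is claimed for site. All power figures use SD 3.36, which Section 8 states for headache days; applying it to migraine headache days is a further assumption. The missing normality criterion is a secondary gap in specification, and naming one method closes it.

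**What to change.** In Section 8, before unblinding:
- Name one primary analysis, two-sided at alpha 0.05: ANCOVA of month-3 migraine headache days on arm, baseline migraine headache days and site, with twice-daily active against twice-daily placebo as the primary contrast.
- State whether the once-daily arm is in the model.
- Reconcile headache days in Section 8 with migraine headache days in Section 7, including the sizing.
- Fix a rule for pooling small sites, for example those that did not complete one batch of six.
- Report the adjusted mean difference with its 95% CI.
- Delete the choice by normality, and keep the t-test and Mann-Whitney on change as sensitivity analyses.

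If the sponsor prefers no adjustment, the minimum is to name one test and its sidedness in advance. The two-sided t-test matches the sizing.

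The cost is wording only: sample size and data collection do not change. The downsides are the pooling rule, a few degrees of freedom (under 0.2 power point for up to 12 assumed sites), up to about 0.5 point if the slope is 1, and a linear model for a bounded count. In the count simulations ANCOVA held type I error at 5.0-5.1%.

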- (iii) Also, women of childbearing age will complete a urine-based pregnancy test to reconfirm that they are not pregnant. The unblinded coordinator will open, at random, an envelope assigning the subject to one of the three study arms. The clinic period is described below. During the first visit, the subject will complete a training session based on a set training module. The subject will complete a proficiency evaluation and the study coordinator will certify the subject's proficiency in the use of the CVS device. The study coordinator will

complete a visit assessment form. At the end of training, a first usability questionnaire will be completed by the subject.

(iv) **First Treatment Period:** The eighty-four days (3 months) following the pre-treatment baseline period constitute the first treatment period. This is the test period, the results from which will be measured against the pre-treatment baseline period data in assessing the study endpoints. Specifically, data from the last month of the first treatment period will be compared with the one-month-long pre-treatment baseline period. As close as possible (as scheduling permits) to two weeks after the start of treatment, a clinical visit will occur and another visit assessment form will be completed. A second usability questionnaire will be completed. The subject will be asked to bring the CVS device to the clinic to perform a treatment in front of the unblinded study coordinator to reaffirm proficiency in using the device. Any issues related to balance or other safety concerns will promptly be referred to the site principal investigator, who can terminate the subject's further participation in the study if necessary.

(v) **End of First Treatment Period – Start of Second Treatment Period:** At the end of the first treatment period the subject will be asked to return to the clinic and will be asked to complete the QOL questionnaires and a third usability questionnaire. All subjects will receive new SD cards for the second treatment period and the old SD cards will be retained so that treatment compliance logs can be extracted. All subjects will receive active treatment cards with the following assignments (first treatment period -> second treatment period):

- BID placebo -> BID active
- BID active -> BID active
- QD active -> QD active

Subjects will perform a treatment in front of the unblinded coordinator to re- confirm their ability to properly use the device.

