BAI (completed)			

BDI-II scores above 20 or **BAI** scores above 16 after treatment has commenced should be referred to the PI for consultation with [name]. If the subject answers in the affirmative to question 9 of the BDI-II form, he/she should be referred for mental health counseling on that same clinic visit.

SUBJECT ID: _____
DATE: _____SITE #: _____
PROTOCOL NUMBER: _____**Device Treatment at the Clinical Site with new Treatment Card:****Yes No**

Was a new Treatment Card (SD card) inserted into the device before treatment?	Yes	No
Any side effects or AEs reported after device treatment?	Yes	No
Was the device treatment aborted?	Yes	No
Any complaints from subject?	Yes	No
Any concerns about the subject?	Yes	No
If Yes, to any questions above, please provide comment:		

- Review device compliance and proper operation of the device and delivery of treatments.
- Administer Usability Questionnaire after completion of device training.
- Review Daily Headache Diary completion and upload to gmail account each day.
- Collect and return old Treatment card (SD card) from the device to Scion NeuroStim (SNS).

I have reviewed the data from this visit and found the information to be complete and accurate. I verify that all of the tasks have been performed.

Principal Investigator Signature

Date

SUBJECT ID: _____
DATE: _____SITE #: _____
PROTOCOL NUMBER: _____**Phone Contact (Week 18)****A phone call to the subject is required every 2 weeks after Initiation of 2nd Treatment Period**

Date of this phone contact	____	/	____	/	____
----------------------------	------	---	------	---	------

Adverse Events and Concomitant Medication Assessment:	Yes	No
Any Adverse Events (AEs) since last visit?		
If Yes, please complete AE form.		
Any new medications or changes in medications since last visit?		
If Yes, please add medication(s) to the Concomitant Medication form. Acute abortive medications and migraine prophylactic medications should not be changed during the clinical trial.		

Subject Compliance:	Yes	No
Is the subject compliant with daily device treatments?		
Is the subject compliant with Daily Headache Diary and uploads?		
If No, to any questions above, please provide comment:		

- Review device compliance and proper operation of the device and delivery of treatments.
- Review Daily Headache Diary completion and upload to gmail account each day.

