6. Have you dropped the device or has it been damaged as far as you know?
 - a. Yes (if yes, do you feel that you created a hazard for yourself or others?)
 - b. No
7. How would you rate your overall experience with the device?
 - a. Very positive
 - b. Somewhat positive
 - c. No opinion
 - d. Somewhat negative
 - e. Very negative
 - f. What are some reasons for your opinion?
8. Do you think that you were in the active treatment group or the placebo group?
 - a. Active
 - b. Placebo
9. Please provide the reason(s) for your answer to question #8.
10. Do you have any final comments to share?

Questionnaire for the End of the second 3-month treatment period:

Date: _____ Subject ID _____

1. Did you find the headset to be comfortable enough to continue with your treatments?
 - a. Yes
 - b. No
2. Did you find that the device is easy to use at home?
 - a. Yes
 - b. No opinion
 - c. It was not easy, but I kept doing it
 - d. No
3. Was the amount of time you spent treating per day:
 - a. Enjoyable
 - b. Acceptable
 - c. No opinion
 - d. Challenging to maintain
 - e. Impossible to maintain
4. Storing the device between uses:
 - a. I had no problem storing the Device safely
 - b. It was challenging to store the Device safely
 - c. I could not store the Device safely

5. Were you able to complete treatments without interruption?
 - a. Yes
 - b. Most of the time
 - c. Not all of the time
 - d. No
6. Have you dropped the device or has it been damaged as far as you know?
 - a. Yes (if yes, do you feel that you created a hazard for yourself or others?)
 - b. No
7. How would you rate your overall experience with the device?
 - a. Very positive
 - b. Somewhat positive
 - c. No opinion
 - d. Somewhat negative
 - e. Very negative
 - f. What are some reasons for your opinion?
8. Do you think that you were in the active treatment group or the placebo group?
 - a. Active
 - b. Placebo
9. Please provide the reason(s) for your answer to question #8.
10. Do you have any final comments to share?

Scion NeuroStim Daily Headache Diary – Baseline Period

- This form is for which calendar date? _____ (day, month, year)
- Did you have a headache today? Yes No
- Do you feel that your headache was a migraine headache? Yes No
- Maximum Pain Level (0-10 scale) on this date: _____
- Duration of any headache (0-24 hours): _____
- Check the box next to any symptoms associated with your headache:
 - Nausea and/or vomiting?
 - Dizziness?
 - Sensitivity to light?
 - Sensitivity to sound?

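### The Visit 4 form lists the arm-guess questionnaire below the first session on the new active card, contrary to section 4(v), so the period-1 blinding guess may be contaminated

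*Combined protocol and SAP*

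**What the plan says.** The arm guess for the first treatment period sits in the usability questionnaire for the end of that period. Item 8 asks "Do you think that you were in the active treatment group or the placebo group", and item 9 asks for the reasons.

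At the same visit every subject changes SD card. Section 4(v) states: "All subjects will receive active treatment cards with the following assignments". The former sham arm is listed as "BID placebo -> BID active".

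Two places describe what happens at this visit:

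- **Section 4(v)** names the questionnaires, then the cards: "will be asked to complete the QOL questionnaires and a third usability questionnaire. All subjects will receive new SD cards for the second treatment period". The observed session is named last: "Subjects will perform a treatment in front of the unblinded coordinator".
- **The Visit 4 form** has a block for the clinic session on the new card, with the check item "Was a new Treatment Card (SD card) inserted into the device before treatment" and items on effects seen after the session. The task list below that block contains "Administer Usability Questionnaire after completion of device training".

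Sections 3 and 5 and the introduction to the usability questionnaires place the guess only at the end of each treatment period. Section 8 plans a descriptive analysis of blinding, with no test or threshold.

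**The concern.** Placebo subjects spend 84 days with unpowered earpieces. Their first session on the new card is also their first real caloric stimulation, running to 42 °C in one ear and 17 °C in the other. Section 6 lists dizziness and vertigo among the more likely effects. Section 3 has subjects told that they will get at least three months of active treatment within the six. A new sensation on a new card then suggests that the earlier card was sham. By the same reasoning, an active subject who notices no change can infer active treatment throughout.

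If the guess is taken after that session, it no longer measures what subjects believed while they kept the diaries. Section 4 treats baseline plus the first treatment period as a complete randomised trial, and its outcome rests on each subject's own judgement of what was a migraine. This is the only direct arm guess that can speak to blinding in that period: by the end of the second period everyone has had active treatment. A contaminated guess could make a sham that worked look as if it had failed, and it cannot be retaken.

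**Working it through.** **1. The order of events, side by side**

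| Source | What it says about order |
|---|---|
| Section 4(v) | Questionnaires, then new cards, then observed session; not stated as a rule |
| Visit 4 form | New-card session block, then a task list containing the questionnaire |
| Sections 3 and 5; usability introduction | End of the period only |
| Schedule of Visits, week 16 | Questionnaire and device treatment at the site both marked; device training not marked |

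The body and the form point in opposite directions. No source says that the guess must precede use of the new card.

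**2. What the form's line can refer to.** The schedule marks device training only at Treatment Day 1 and the week 7 visit. At week 16 the only scheduled device activity is the new-card session. Read as an instruction for that visit, the line therefore points to a time after that session. The same line stands on the forms for Visits 2 and 3, where it does no harm: the questionnaires used there contain no arm guess, and no card has been switched. It looks carried over to a visit where the order does matter.

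**3. Size, by assumption only.** The documents give no guess rates. The plan's one numerical design figure, 40 per arm, reproduces from its stated inputs (two-sided 0.05 assumed, since sidedness is not stated): 2 × (1.96 + 0.84)² × 3.36² / 2.13² = 39.0, so 40. It does not depend on this point and serves here only as the arm size.

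Assume that placebo subjects would otherwise guess 50:50, and that a share f of them recognise the change and answer placebo.

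- Correct guesses: p = f + (1 − f) × 0.5 = 0.5 + f/2
- Bang blinding index: 2p − 1 = f
- Standard error: 2 × √(p(1 − p)/n), with n = 40

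For f = 0.25: p = 0.625, SE = 2 × √(0.625 × 0.375/40) = 0.153, and the 95% interval is 0.25 ± 1.96 × 0.153.

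| f (assumed) | Correct guesses | Bang index | 95% interval |
|---|---|---|---|
| 0 | 50% | 0 | −0.31 to 0.31 |
| 0.10 | 55% | 0.10 | −0.21 to 0.41 |
| 0.25 | 62.5% | 0.25 | −0.05 to 0.55 |
| 0.50 | 75% | 0.50 | 0.23 to 0.77 |

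The same formula applies to an active arm, with f replaced by the share who infer active treatment from noticing no change.

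**4. What is outside the reach of the problem.**

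- Treatment runs over weeks 5 to 16, so the third-month diary entries (weeks 13 to 16) precede a session held at the end of week 16.
- The quality-of-life forms come before the new-card session in both section 4(v) and the Visit 4 form.
- The questions asked after the very first clinic session were answered at the start of treatment.

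**The case against.** The strongest reply is that the form does not fix an order. Its line speaks of training, not of the new-card session. Training was finished long before week 16, so a site that gives the questionnaire first still complies literally. The task list is not strictly chronological either: collecting the old card comes last, although the new one must go in before the session. Section 4(v) already names the safe order, and item 8 is worded in the past tense. Item 9 might show when an answer was driven by that day's session. The protocol attaches its wording about evidence of an effective sham to the first-session questions, which are untouched.

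Most of this stands, and it limits the point to a conflict that has to be resolved. It does not remove the point. Section 4(v) does not make its order a rule, and staff at the visit work from the form. The first-session questions ask about sensations, not about arm, so they cannot replace the guess.

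A reader might go further and infer that the blinding check is biased, that the distortion falls on placebo subjects alone, or that nearly all of them would guess correctly. The documents support none of these. The order that sites follow is not known, active subjects may also learn something from the session, and no guess rate or recognition rate is given. Nor can it be inferred that the efficacy data are compromised, because the third-month diary data and the quality-of-life forms come before the session.

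**Conclusion.** The point holds in conditional form. The Visit 4 form and section 4(v) disagree on whether the arm guess comes before or after the first session on the new active card, and nothing settles it. If sites follow the form's layout and subjects notice the switch, or its absence, the period-1 guess may be contaminated. The size cannot be derived from the documents; the illustrative figures rest wholly on an assumed 50:50 start and assumed recognition shares. On those assumptions, a quarter recognising the switch would leave an interval for the blinding index that still includes zero, while half would not. What is at risk is the evidence that the first period was blinded, not the primary endpoint data, the quality-of-life scores or the sample size. It should be corrected before the first subject reaches Visit 4, because the guess cannot be repeated after exposure.

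**What to change.** Reconcile the Visit 4 form with section 4(v):

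1. On the form, move the end-of-first-period usability questionnaire, or at least items 8 and 9, above the device-treatment block.
2. Replace the carried-over reference to device training with an instruction that the questionnaire must be completed before the new SD card is inserted, and state the same rule in section 4(v).
3. Record the time of completion, so that the blinding analysis can show that each guess came before the session.

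The cost is one form edit, one sentence in the protocol and one extra time field. Sample size, visit schedule and efficacy analysis do not change.
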